# List of abbreviations

Acronym	Details
AE	Adverse event
AF	Autofluorescence
AKI	Acute kidney injury
BCVA	Best corrected visual acuity
CEN	Central optical involvement
CF	Counting fingers
CI	Confidence interval
CMT	Central macular thickness
COR	Cortical
CRF	Case report form
CSCR	Central serous chorio-retinopathy
CSRT	Central subfield retinal thickness
CTEU	Clinical Trials and Evaluation Unit
DBP	Diastolic blood pressure
DMSC	Data monitoring and safety committee
eGFR	Estimated glomerular filtratin rate
ETDRS	Early treatment diabetic retinopathy study
FFA	Fundus fluorescein angiogram
FP	Fundus photography
GM	Geometric mean
GMR	Geometric mean ratio
Hct	Haematocrit
HM	Hand movements
HR	Hazard ratio
ICGA	Indocyanine green angiography
IQR	Inter quartile range
ITT	Intention to treat
LP	Light perception
MAR	Missing at random
MD	Mean difference
NLP	No light perception
NUC	Nuclear sclerosis
OCT	Optical coherence tomography
OR	Odds ratio
PDT	Photodynamic laser therapy
PH	Proportional hazards
PIL	Patient information leaflet
PSC	Posterior subcapsular
RCT	Randomised controlled trial
RPE	Retinal pigment epithelium
SAE	Serious adverse event
SAP	Statistical analysis plan
SBP	Systolic blood pressure

Acronym	Details
SD	Standard deviation
SFF	Subfoveal fluid
SRF	Subretinal fluid
TR	Time ratio
VA	Visual acuity
VFQ	Visual function questionnaire

# 1. INTRODUCTION TO SAP

### 1.1 Scope

This statistical analysis plan (SAP) details information regarding the statistical analysis of the VICI randomised controlled trial (RCT) and covers all analyses of study data outlined in the study protocol.

#### **1.2 Editorial changes**

Any changes made to this SAP after approval must be clearly justified and documented as an amendment at the end of this document. The SAP should then be re-approved.

### 1.3 SAP document approval

The co-director of the Clinical Trials and Evaluation Unit (CTEU) must authorise this document.

#### 1.4 Skeleton tables and figures

Throughout this document references are made to skeleton tables and figures to be used in the reporting of the study (e.g. **Figure F1** or **Table T1**). Such tables and figures can be found in **Appendix A** of this document and are intended as a guide for study reporting. Final versions of the tables/figures may differ: tables may be combined, and/or their layout or numbering may differ. However, the content should be consistent with **Appendix A**.

# 2. STUDY BACKGROUND AND OBJECTIVES

#### 2.1 Study background

The VICI study is a multi-centre double-blind parallel-group RCT. It aims to test the superiority of eplerenone therapy with usual care to placebo with usual care in adult patients with chronic central serous chorio-retinopathy (CSCR).

#### 2.2 Study objectives

The primary objective is to evaluate whether best corrected visual acuity (BCVA) following eplerenone therapy with usual care is superior to placebo with usual care in eyes with chronic CSCR.

Secondary objectives are:

- (a) To evaluate whether eplerenone treatment with usual care is better than placebo with usual care for resolution of subretinal fluid (SRF)
- (b) To describe the safety profile of eplerenone treatment with usual care (compared to placebo with usual care)
- (c) To evaluate whether participant-reported visual function improves with eplerenone treatment with usual care compared to placebo with usual care
- (d) To describe how the choroid responds to treatment in CSCR
- (e) To describe how retinal pigment epithelium (RPE) function changes over a year in CSCR as measured by autofluorescence (AF)
- (f) To evaluate how low luminance visual acuity changes with eplerenone treatment

#### 2.3 Primary outcome

The primary outcome is BCVA over a 12 month period.

#### 2.4 Secondary outcomes

Secondary outcomes are listed in the study protocol as:

- (1) Low luminance BCVA over a 12 month period.
- (2) Central subfield retinal thickness (CSRT) as measured by optical coherence tomography (OCT) over a 12 month period
- (3) Change in SRF thickness as measured by OCT
- (4) Adverse events at any time during the 12-month follow-up period
- (5) Proportion of patients with macular atrophy of the RPE defined as hypoautofluorescence at 12 months
- (6) Area change in macular RPE hypoautofluorescence at 12 months
- (7) Choroidal thickness as measured by enhanced depth imaging OCT over a 12 month period
- (8) Proportion of patients with reduced choroidal permeability on indocyanine green angiography (ICGA) at 12 months
- (9) Time to resolution of SRF
- (10) Classification of all study eyes as complete, partial or no resolution of SRF at each time point of the study

- (11) Patient-reported visual function using Visual Function Questionnaire VFQ 25 at 12 months adjusted for baseline
- (12) Classification of all study eyes by each fundus fluorescein angiogram (FFA) phenotype
- (13) Classification of all study eyes as early, late, or non-responder
- (14) Incidence of CSCR in the fellow eye
- (15) Time to disease recurrence

#### How secondary objectives link to secondary outcomes

Secondary objectives are as below. In parentheses are the secondary outcome(s) linked to the objective.

- (a) To evaluate whether eplerenone treatment with usual care is better than placebo with usual care for resolution of SRF [3,9,10,13]
- (b) To describe the safety profile of eplerenone treatment with usual care (compared to placebo with usual care) [4]
- (c) To evaluate whether participant-reported visual function improves with eplerenone treatment with usual care compared to placebo with usual care [11]
- (d) To describe how the choroid responds to treatment in CSCR [7,8]
- (e) To describe how RPE function changes over a year in CSCR as measured by autofluorescence (AF) [5,6]
- (f) To evaluate how low luminance visual acuity changes with eplerenone treatment [1]

#### 2.5 Exploratory analyses

Additional exploratory analyses of the overall trial cohort will investigate:

- (1) The association between final visual acuity and age of the patient
- (2) The association between presence of granular/confluent hypoautofluorescence in the macula at randomisation and final visual acuity.

#### 2.6 Changes to the study objectives during the course of the study

There have been no changes to the study objectives during the course of the study. OCT angiography was added partway through the study and is only available for a subset of participants being treated at centres where OCT angiograph equipment is available.

# 3. STUDY POPULATION

The study population is all patients recruited into the trial satisfying the main eligibility criteria: aged between 18 and 60 years who have had visual impairment due to CSCR for at least four months (defined as subfoveal presence of SRF on OCT, characteristic appearance of CSCR on FFA and ICGA, and an investigator believes there is sufficient evidence that CSCR has been present for at least 4 months). For specific inclusion/exclusion criteria see **Figure F1**.

Recruitment over time against targets will be presented overall (Figure F2).

The planned sample size for the VICI study is 104 patients. This sample size is sufficient to detect a difference of 5 letters in BCVA between the eplerenone and placebo groups with 90% power and 5% significance (2-tailed), assuming that: the standard deviation is 9 letters; the correlation between baseline and any follow up assessment is 0.5; on average, there will be a minimum of 2 follow up assessments per patient with a correlation between BCVA on follow-up visits of 0.8; up to 15% dropout will occur over the 12 month period.

#### 3.1 Flow of participants

Participant flow will be described via a flowchart (see **Figure F1**). Follow-up will last 12 months with follow-up visits planned at 1 week, 4 weeks, 3 months, 6 months, 9 months and 12 months post-randomisation.

#### 3.2 Randomisation

Patients are randomised (1:1 ratio) to either eplerenone with usual care or placebo with usual care. Randomisations are in blocks of varying size and stratified by study centre and visual acuity level (high/low). Randomisation should take place within one month of the screening visit. The sequence of random allocations were generated by a computer in advance of starting to recruit.

#### 3.3 **Protocol deviations**

The following will be considered a protocol deviation:

- Patient received the alternative drug to that allocated on at least one occasion
- Patient did not meet the study eligibility criteria but was treated in the study
- Patient did not attend a study visit (prior to study exit)
- Visit attended but outside of visit window
- Patients potassium exceeded 5.0mmol/L but patient was informed to continue treatment
- Incorrect dosage regimen followed
- Patient prescribed more medication than required at study visit
- Patients disease resolved but informed to continue treatment

Note it may be possible for patients to be classified as a protocol deviation for more than one reason.

The frequency of each type of deviation will be tabulated by treatment allocation (see **Table T1**).

### 3.4 Withdrawals

A patient (or a clinician on their behalf) can withdraw from the study at any time. Data from participants who consent to data collected prior to withdrawal being used will be included up to the point of withdrawal. Participants who do not consent to their data collected in the trial being used will be excluded, see **section 3.5** for further details.

Data on all withdrawals is captured on a specific case report form (CRF) and will be tabulated by treatment allocation; see **Table T2**.

#### 3.5 Analysis population

The analysis population consists of all randomised patients excluding:

- Patients who died after randomisation but prior to any data collection.
- Patients withdrawn who were unwilling for data collected to be used.

The main study analyses will be performed on a (modified) ITT basis, modified to take into account exclusions listed above.

#### 3.6 Safety population

The safety population is the same as the analysis population for the VICI trial. Participants will be grouped according to the treatment allocated and events in participants who were non-compliant, received the alternative treatment (e.g. study drug received by participant randomised to placebo or vice versa) or received no treatment will be detailed in footnotes.

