### 4.3 Other variables

Details for any other variables which will be derived for use in any other figures or tables are given below:

New variable	Rules
Exclusion category	INELIGIBLE: any of the inclusion criteria are NO, or any of the exclusion criteria are YES NOT APPROACHED: patient is eligible, patient approached = NO DID NOT CONSENT: patient is eligible, patient approached = YES, patient consented = NO DID NOT ATTEND SCREENING VISIT: patient is eligible, patient approached = YES, patient consented = YES, screening visit attended = NO INELIGIBLE POST-CONSENT: patient is eligible, patient approached = YES, patient consented = YES, screening visit attended = YES, patient consented = YES, screening visit attended = YES, patient consent = YES, screening visit attended = YES, but any of the post-consent inclusion criteria = NO, or any of the post-consent exclusion criteria = YES OTHER: patient is eligible, patient approached = YES, patient consented = YES, screening visit attended = YES, post- consent eligibility = YES, randomised = NO
Treatment received	YES: if at least one prescription has been completed NO: if no prescriptions have been completed
Age (years)	= (date of randomisation – date of birth)/365.25
Protocol deviation 1 – patient received the alternative drug to that allocated on at least one occasion	YES: if a bottle on any prescription does not match their treatment allocation NO: if all bottles on all prescriptions match their treatment allocation MISSING: otherwise
Protocol deviation 2 – patient did not meet eligibility criteria but was treated in the study	YES: if patient was ineligible at screening visit or at post- consent visit but was randomised NO: if patient was eligible MISSING: otherwise Note: if a patient who was otherwise eligible was ineligible due to an allergy to fluorescein or indocyanine green, a decision was made by the chief investigator to include them in the study, allowing them to take part in all aspects except for the FFA or ICGA imaging. These patients will not be classed as a protocol deviation.
Protocol deviation 3 – missed visit	YES: if patient attended visit = NO for any of the study visits before study exit) NO: if patient attended visit = YES for all study visits (before study exit) MISSING: otherwise

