#### 5.4 Safety data

Adverse events (AEs) occurring in the study period for all patients in the safety population will be tabulated as per **Table T19 to T21**.

**Table T19** summarises expected AEs listed in the study protocol, with events that meet the serious criteria indicated. Such events are captured via the study CRFs.

Table T20 provides further details on the expected AEs that meet the serious criteria.

**Table T21** summarises unexpected serious adverse events (SAEs), i.e. events that are not listed in the study protocol that meet the serious criteria. Such events are captured via separate SAE report forms.

No formal comparisons between treatment groups will be made, as numbers of events are expected to be small.

<sup>1 An event is classified as serious if it meets one or more of the following criteria: a) resulted in death, b) was life threatening, c) resulted in persistent or significant disability/incapacity, d) prolonged an ongoing hospitalisation or resulted in hospitalisation

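### The safety population inherits an exclusion of some post-randomisation deaths, so a death meeting that rule cannot enter the adverse event tables

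*SAP*

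**What the plan says.** Three sections of the SAP act together.

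- **Section 3.5** defines the analysis population as all randomised patients less two groups: "Patients who died after randomisation but prior to any data collection" and "Patients withdrawn who were unwilling for data collected to be used".
- **Section 3.6** adds: "The safety population is the same as the analysis population for the VICI trial". It continues: "Participants will be grouped according to the treatment allocated". Events in participants who were non-compliant, received the other arm's drug or "received no treatment will be detailed in footnotes".
- **Section 5.4** says: "Adverse events (AEs) occurring in the study period for all patients in the safety population will be tabulated". Its footnote on seriousness lists a fatal outcome as criterion (a). The section cites the tables as T19 to T21; Appendix A numbers them T21 to T23, and those numbers are used here.

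Section 4.2 item 4, which covers the adverse event outcome, says without exception that all adverse events at any time in the 12-month follow-up will be reported. Table T2 (withdrawals) has a row for patients who died.

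**The concern.** An exclusion for death before data collection may do little harm in an efficacy set, because there may be no outcome to analyse. In a safety set the death is itself the observation. A rule that removes participants because they died removes them from numerator and denominator alike, and could do so in one arm only.

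Secondary objective (b) is to describe the safety profile of eplerenone. Section 5.4 plans no formal comparison, so the descriptive tables carry that objective alone. If a death is missing from them, no later analysis brings it back.

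**Working it through.** **1. Following one participant through the text.** Take a participant who is randomised and dies before any data are collected, in whatever sense the SAP intends.

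- 3.5: excluded from the analysis population.
- 3.6: therefore excluded from the safety population.
- 5.4: the AE and SAE tables cover the safety population, so the death is not in T21, T22 or T23.
- 4.2 item 4: the death falls within the 12-month follow-up and should be reported as an adverse event.
- T2: the death can appear as a reason for withdrawal. This table also counts withdrawals before randomisation, so it is not confined to the analysis population. It gives neither intensity nor relatedness, which T22 does.

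The first three steps and the fourth cannot both hold for this participant.

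**2. Who meets the rule?** The SAP does not say which data count.

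| Reading | What the SAP shows | Deaths excluded |
|---|---|---|
| Any data, baseline included | Visual acuity level is a stratification factor (3.2); randomisation factors are complete by design (5.3.8); BCVA is measured at baseline (4.1); blood pressure and heart rate come from screening or baseline (4.3) | Almost none |
| Post-randomisation follow-up data only | First follow-up visit is at 1 week (3.1) | Those before about the 1-week visit |

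The rule is therefore either nearly empty or removes early deaths from safety reporting.

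**3. Arm size.** The plan's own figure is checked first. Inputs from section 3: difference 5 letters, SD 9, baseline to follow-up correlation 0.5, two follow-ups correlated 0.8, 90% power, two-sided 5%, 15% dropout.

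- Variance factor: (1 + (2 − 1) × 0.8)/2 − 0.5² = 0.90 − 0.25 = 0.65.
- Per arm: 2 × [9 × (1.960 + 1.282)/5]² × 0.65 = 44.26.
- Total with dropout: 2 × 44.26/0.85 = 104.1, against 104 stated.

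The figure reproduces. With 1:1 allocation it gives 104/2 = 52 per arm. It serves only as the denominator below.

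**4. Size on the second reading.** Assume one excluded death in one arm; the SAP gives no expected count.

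- Counted: 1/52 = 1.9% (exact 95% CI 0.05% to 10.3%).
- Excluded: 0/51 = 0% (exact upper limit 7.0%).

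**5. Never-treated participants in the denominators.** Suppose k of 52 never start and have no events, and the event rate among the treated is 10%. The reported rate is 10% × (52 − k)/52:

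| k | Reported rate |
|---|---|
| 1 | 9.8% |
| 2 | 9.6% |
| 3 | 9.4% |
| 5 | 9.0% |

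The dilution is small over this range.

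**The case against.** The strongest reply is that the exclusion, read literally, has almost no effect. A participant who was prescribed drug already has a stratum, a baseline assessment and a prescription record, so that participant has collected data and stays in. Section 5.3.8 supports this reading: longitudinal baseline values are modelled jointly with follow-up, so one observation is enough for inclusion. Early death is also unlikely at ages 18 to 60, and T2 has a row for it.

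Much of this stands, and it limits the point. A reader might infer that anyone who dies soon after randomisation is lost from the safety tables. The text does not say that: the condition is death before any data collection, however early or late. A reader might also infer that the exclusion was written with visual acuity in mind; the SAP gives no reason for it. What the reply leaves untouched is that the term is undefined, and that on neither reading does the exclusion serve a safety population.

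A further tempting inference is that keeping never-treated participants and grouping by allocation are errors. They are stated choices with footnoted events, and Table T21 repeats the footnote for events off treatment. The footnotes do not change the denominators, but step 5 shows how little that matters. An as-treated set would bring problems of its own:

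- *Treatment received* is set by this rule: "YES: if at least one prescription has been completed". It does not show that a tablet was taken.
- Protocol deviation 1 is triggered by a single mismatched bottle, so a flagged participant may have had both treatments, and the treatment actually received is then not defined.
- Requiring a prescription would drop a death that occurred before the first one.

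**Conclusion.** The point holds in a limited form. By its own wording the SAP keeps any death that meets the section 3.5 rule out of T21 to T23, and this conflicts with section 4.2 item 4. Whether that could touch a real participant depends on an undefined term: almost nobody if baseline data count, deaths before about the 1-week visit if they do not. The shift from 1/52 to 0/51 assumes the second reading and one death in an arm of 52; it illustrates the effect and is not a forecast. The documents do not support a claim that early deaths in general are removed, or that the allocation-based grouping is wrong. The change is still worth making, because it removes a rule that a safety population does not need.

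**What to change.** In section 3.6, replace the cross-reference with a separate definition: all randomised participants except those who refuse use of their data, without the exclusion for death. Add that every post-randomisation death in this population is tabulated in T21 and in T22 or T23, whether or not other data were collected. If section 3.5 keeps its death exclusion for efficacy, state there which data count. Correct the table numbers in section 5.4 at the same time.

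Grouping by allocation with footnotes may stay. As an option, show per arm, beside the AE denominators, how many participants were never treated and how many received the other arm's drug.

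The cost is a few sentences in a SAP amendment. Safety and efficacy denominators may differ slightly, which a footnote can explain.

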# 4. DERIVATIONS

#### 4.1 **Primary outcome**

The primary outcome is the BCVA in the study eye over a 12-month period. BCVA is measured at baseline, 4 weeks, 3, 6, 9 and 12 months, using validated Early Treatment Diabetic Retinopathy Study (ETDRS) vision charts with measurements made in accordance with a standardised protocol for trials in medical retina.

New variable	Rules
BCVA at standard luminance (study	At each visit:
eye)	
 
ETDRS letters read at standard luminance in study eye if ETDRS letters read at standard luminance not missing; OR
 

	= 0 if ETDRS letters read at standard luminance in study eye = missing AND count fingers = YES; OR
	
 
-15 if ETDRS letters read at standard luminance
 
in study eye = missing AND hand movements =
 
YES; OR
 

	
 
-30 if ETDRS letters read at standard luminance
 
in study eye = missing AND perception of light =
 
YES; OR
 

	
 
-45 if ETDRS letters read at standard luminance in study eye = missing AND perception of light = NO; ELSE
 

	= MISSING

A value of zero equates to no letters read at 1 metre. The other values (which equate to a doubling of the visual angle) are chosen to allow approximate numbers of letters to be assigned to the commonly-used categories of deteriorating visual function.

#### 4.2 Secondary outcomes

#### 1. BCVA at low luminance

Low luminance BCVA is measured in the study eye immediately after measuring BCVA and is measured at baseline, 4 weeks, 3, 6, 9 and 12 months.

New variable	Rules
BCVA at low luminance (study eye)	At each visit:
	
 
ETDRS letters read at low luminance in study eye if ETDRS letters read at low luminance not missing; OR
 

	= 0 if ETDRS letters read at low luminance in study eye = missing AND count fingers = YES; OR
	
 
-15 if ETDRS letters read at low luminance in study eye = missing AND hand movements = YES; OR
 

	
 
= -30 if ETDRS letters read at low luminance in study eye = missing AND perception of light = YES; OR
 

 -45 if ETDRS letters read at low luminance in study eye = missing AND perception of light = NO; ELSE
 = MISSING

#### 2. CSRT

CSRT is measured in the study eye by OCT and is measured at baseline, 4 weeks, 3, 6, 9 and 12 months. CSRT is recorded directly (variable name: SE\_OCT\_CentralSubfieldRetinalThickness) and so no derivation is required.

#### 3. Change in sub-retinal fluid thickness

Sub-retinal fluid thickness is measured in the study eye by OCT. Measurements at baseline and 12 months will be used to derive this outcome. Change in sub-retinal fluid thickness will be described; sub-retinal fluid thickness at 12 months will be compared between groups, adjusting for baseline.

New variable	Rules	
Sub-retinal fluid thickness (study eye)	If 'Is maximum SRF at fovea?' (SE_OCT_IsMaxSRFAtFovea) = YES; then = 'Height of SRF at fovea' (SE_OCT_HeightSRFAtFovea) Else if 'Is maximum SRF at fovea?' = NO; then = 'If no, measure height of maximum SRF' (SE_OCT_HeightMaxSRF) Else = Missing	
Change in sub-retinal fluid thickness	
 
= (sub-retinal fluid thickness at 12 months – sub-retinal fluid thickness at baseline)
 
	

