#### 9. Time to resolution of SRF

Resolution of SRF will be assessed in the study eye at 4 weeks, 3, 6, 9 and 12 months.

New variable	Rules
SRF resolved (study eye)	YES: if 'Are there any areas of hyporeflectivity
	separating the neurosensory retina and the
	RPE/Bruch's Complex on any scan?'
	(SE_OCT_HyporeflectivityOnAnyScan) = NO
	NO: if 'Are there any areas of hyporeflectivity
	separating the neurosensory retina and the
	RPE/Bruch's Complex on any scan?' = YES
	MISSING: otherwise
Time to resolution of SRF (study eye)	= (Date of SRF resolution – date of randomisation)

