#### 10. Classification of study eyes as complete, partial or no resolution of SRF

Classification of study eyes will be completed at each time point of the study. Partial resolution of SRF is defined as a decrease of >25% of CMT from baseline due to resolution of SRF. A non-responder is defined as having an increase in SRF or decrease in SRF  $\leq 25\%$  from baseline.

New variable	Rules
Central macular thickness (study eye)	Central subfield retinal thickness (SE_OCT_CentralSubfieldRetinalThickness)
Resolution of SRF (study eye)	COMPLETE RESOLUTION: if SRF has completely resolved
	PARTIAL RESOLUTION: if CMT has decreased by >25% from baseline
	NON-RESPONDER: if SRF increased or decreased by ≤25% from baseline
	MISSING: if CMT missing

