#### Missing predictors:

There will be no missing data for any of the randomisation factors (by design). All other potential predictors are baseline measurements of continuous longitudinal outcomes, and due to the modelling approach described previously the handling of missing values for such data is considered in the context of missing longitudinal data (see below).

Missing outcomes measured at one time point:

• If the proportion of missing data is less than 5% then complete case analysis will be performed (i.e. excluding cases with missing data).

 If the proportion of missing data is above 5% multiple imputation methods will be considered. A general imputation model that uses an iterative procedure to generate imputed values will be used to generate multiple complete data sets (e.g. using Stata's mi impute). The model of interest will be the fitted to each of the complete data sets and effect estimates combined using Rubin's rules. If appropriate, methods such as predictive mean matching will be used in order to ensure that imputed values lie within specific ranges.

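### The SRF-thickness derivation has no rule for an eye without fluid, so unless the grading form records a height of 0, resolved eyes become missing in the 12-month comparison

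*SAP*

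**What the plan says.** SAP section 4.2, item 3, derives SRF thickness in the study eye in three steps. The first is "If 'Is maximum SRF at fovea?' (SE_OCT_IsMaxSRFAtFovea) = YES; then = 'Height of SRF at fovea' (SE_OCT_HeightSRFAtFovea"). If the answer is NO, the maximum height is used, and everything else is missing: "then = 'If no, measure height of maximum SRF' (SE_OCT_HeightMaxSRF) Else = Missing". The planned analysis is that "sub-retinal fluid thickness at 12 months will be compared between groups, adjusting for baseline".

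Item 9 of the same section (time to resolution of SRF) defines a resolved eye from a different OCT field: "SE_OCT_HyporeflectivityOnAnyScan) = NO". Item 10 gives complete resolution its own category, "if SRF has completely resolved".

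Section 5.3.8 has two rules for an outcome measured at one time point. The first is "If the proportion of missing data is less than 5% then complete case analysis will be performed". The second is "If the proportion of missing data is above 5% multiple imputation methods will be considered"; it adds that predictive mean matching may be used where appropriate.

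Section 5.3.2 and Table T17 allow this outcome to be reported either as a difference in means or, after log transformation, as a geometric mean ratio.

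**The concern.** The question whether the maximum fluid is at the fovea presupposes that there is fluid. In a dry eye it has no natural answer, and on a plain reading of the rule such an eye falls through to missing. Its thickness is not unknown, however. It is 0, and the item 9 field says so.

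The gap matters mainly after randomisation. Eligibility requires subfoveal SRF on OCT (section 3), so the rule should generally work at baseline. At 12 months it can fail for exactly the eyes with the best result. Missingness would then depend on the outcome, and on treatment too if treatment clears fluid. The outcome is formally compared, and section 2.4 links it to secondary objective (a), resolution of SRF.

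**Working it through.** **1. Trace of the rule for an eye that is dry at 12 months.**

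| What the form holds for the dry eye | Thickness returned |
|---|---|
| Fovea question YES, foveal height 0 | 0 |
| Fovea question NO, maximum height 0 | 0 |
| Fovea question YES or NO, height blank | no value |
| Fovea question blank or not applicable | Missing |

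The SAP does not say which row applies. `SE_OCT_HyporeflectivityOnAnyScan` would settle the matter in every row, but item 3 does not use it.

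**2. Comparison with the BCVA rule.** Section 4.1 assigns a number when no letter score exists, for example "0 if ETDRS letters read at standard luminance in study eye = missing AND count fingers = YES; OR". Item 3 has no equivalent step.

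**3. What section 5.3.8 would then do.** The SAP plans 104 patients with up to 15% dropout: 104 × 0.85 = 88.4, or about 88 evaluable eyes. Even with no other missing data, 4/88 = 4.5% is below the 5% threshold and 5/88 = 5.7% is above it.

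- Up to four resolved eyes set to missing: they are dropped.
- Five or more: multiple imputation is considered. If every dry eye is missing, all observed 12-month values are positive. Predictive mean matching takes its values from observed eyes, so it would give a positive height to an eye whose thickness is 0.

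**4. Illustration of size.** The SAP gives no figures for SRF thickness, so every input here is an assumption: 44 eyes per arm; mean height m = 100 µm in unresolved eyes of both arms; treatment acting only by raising the proportion resolved, from p_C (placebo) to p_T (eplerenone).

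- Resolved eyes coded 0: difference = m(1 − p_T) − m(1 − p_C) = −m(p_T − p_C).
- Resolved eyes missing and dropped: difference = m − m = 0.
- Eyes lost = 44(p_C + p_T).

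The power columns come from 4,000 simulated trials per row (heights with SD 50 µm, unadjusted t-test at two-sided 5%).

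| Resolved, placebo vs eplerenone | Difference with zeros | Difference if dropped | Eyes lost of 88 | Power with zeros | Rejection rate if dropped |
|---|---|---|---|---|---|
| 10% vs 30% | −20 µm | 0 | 17.6 | 37% | 5% |
| 20% vs 40% | −20 µm | 0 | 26.4 | 34% | 5% |
| 30% vs 50% | −20 µm | 0 | 35.2 | 33% | 5% |
| 20% vs 50% | −30 µm | 0 | 30.8 | 63% | 5% |

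With SD 60 µm and skewed (gamma) heights, the 20% vs 40% case gives the same differences, and power with zeros is about 28%.

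**5. Direction is not fixed.** Suppose instead that eyes with thinner fluid resolve more readily (assumed latent correlation 0.5, SD 60 µm). At 20% vs 40%, the difference with zeros is about −17 µm; dropping resolved eyes gives about +9 µm, an apparent disadvantage. If treatment also lowered height in unresolved eyes, the estimate after dropping would not be 0 either.

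**The case against.** The strongest reply is that the grading form is not shown. If graders enter YES or NO with height 0 for a dry eye, the rule already returns 0 and nothing is lost. That stands, and it makes the harm conditional.

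Three stronger readings are tempting, and the document does not support them.

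- A reader might infer that resolved eyes certainly become missing. That depends on the form.
- A reader might infer that the comparison is made only among unresolved eyes. That describes complete-case analysis, which section 5.3.8 prescribes only below 5% missing. Above that, imputation is to be considered, and the model is not specified closely enough to say what it would return.
- A reader might extend the point to the area of hypoautofluorescence (item 6). That rule takes the recorded area directly, with no YES/NO gate and no default to missing, so a recorded 0 passes through.

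The illustration also has limits. Its zero follows from giving unresolved eyes the same heights in both arms. It uses an unadjusted test, whereas the SAP plans regression adjusted for baseline, and it does not model imputation.

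Finally, objective (a) does not rest on this outcome alone. Outcomes 9, 10 and 13 also capture clearance of fluid, and outcome 9 reads the dry-eye field directly. Section 5.3.8 also requires missing data to be footnoted and the reasons for a substantial imbalance to be explored, so a large gap between arms should be noticed.

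None of this supplies the absent branch. Footnotes would show the pattern without correcting it, and the missing-value sensitivity analysis in section 5.3.7 covers binary outcomes only.

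**Conclusion.** The point holds in conditional form. The written rule has no branch for an eye without SRF. Unless the form records a height of 0, a known zero becomes missing because of the outcome, and neither dropping such eyes nor imputing them from eyes with fluid repairs the comparison.

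Neither the size nor the direction of the bias can be computed from the SAP. Under the assumptions shown, a true difference of 20 to 30 µm in favour of treatment is estimated as about 0, and it can change sign if thinner fluid clears first.

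The importance is moderate. This is one secondary outcome, clearance is measured in other ways too, and neither the primary outcome nor the sample size of 104 is touched. It is still worth correcting before analysis, because a derivation should not depend on an undocumented grading convention when one of the possible conventions removes the best outcomes.

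**What to change.** In section 4.2, item 3, add as the first line of the rule: thickness = 0 if `SE_OCT_HyporeflectivityOnAnyScan` = NO at that visit. Reserve missing for an absent or ungradable OCT.

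Zeros cannot be logged, so section 5.3.2 should also state how they are handled if the log transformation and geometric mean ratio are used for this outcome, with a matching note in Table T17.

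The cost is one line in a derivation table and one sentence on zeros, recorded as a SAP amendment under section 1.2. No new data are needed. If dry eyes are already recorded with height 0, no derived value changes.
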